9. STATISTICAL METHODOLOGY

9.1 General

Data listings will be provided for all data that is databased. Summary statistics and statistical analysis will only be presented for data where detailed in this SAP. For continuous data, summary statistics will include the arithmetic mean, arithmetic standard deviation (SD), median, min, max and N; for log-normal data (e.g. the PK parameters: AUCs and C_{max}) the geometric mean and geometric CV% will also be presented. For categorical data, frequency count and percentages will be presented. Data listings will be provided for all subjects up to the point of withdrawal, with any subjects excluded from the relevant population highlighted. Summary statistics and statistical analyses will generally only be performed for subjects included in the relevant analysis population. For the calculation of summary statistics and statistical analysis, unrounded data will be used.

Mean change from baseline is the mean of all individual subjects' change from baseline values. Each individual change from baseline will be calculated by subtracting the individual subject's baseline value from the value at the timepoint. The individual subject's change from baseline values will be used to calculate the mean change from baseline using a SAS procedure such as Proc Univariate.

Data analysis will be performed using SAS[®] Version 9.4 or greater.

9.2 Demographics and Subject Disposition

Subject disposition will be listed. The demographic variables age, sex, race, ethnicity, country of enrolment, site ID, body weight, height and body mass index will be summarized and listed.

All other demographic variables will be listed only.

9.3 Pharmacokinetic Assessment

9.3.1 Pharmacokinetic Analysis

The PK parameter estimates will be determined using non-compartmental procedures in validated software program (Phoenix WinNonlin Version 8.1 or later).

Serum concentrations of LY3074828 will be used to determine the following PK parameters, when possible:

Parameter	Units	Definition
AUC(0-t _{last})	day* μ g/mL	area under the concentration versus time curve from time zero to time t, where t is the last time point with a measurable concentration
AUC(0-∞)	day* μ g/mL	area under the concentration versus time curve from time zero to infinity
%AUC(t _{last} -∞)	%	percentage of AUC(0-∞) extrapolated
C _{max}	μ g/mL	maximum observed drug concentration
t _{max}	day	time of maximum observed drug concentration
t _{1/2}	day	half-life associated with the terminal rate constant (λ_z) in non-compartmental analysis
CL/F	L/day	apparent total body clearance of drug calculated after extra-vascular administration
V _{Z/F}	L	apparent volume of distribution during the terminal phase after extra-vascular administration
V _{ss/F}	L	apparent volume of distribution at steady state after extra-vascular administration

Additional PK parameters may be calculated, as appropriate. The software and version used for the final analyses will be specified in the clinical study report. Any exceptions or special handling of data will be clearly documented within the final study report.

Formatting of tables, figures and abbreviations will follow the Eli Lilly Global PK/PD/TS Tool: NON-COMPARTMENTAL PHARMACOKINETIC STYLE GUIDE. The version of the tool effective at the time of PK analysis will be followed.

General PK Parameter Rules

- Actual sampling times will be used in the final analyses of individual PK parameters, except for non-bolus pre-dose sampling times which will be set to zero.
- C_{max} and t_{max} will be reported from observed values. If C_{max} occurs at more than one time point, t_{max} will be assigned to the first occurrence of C_{max}.
- AUC parameters will be calculated using a combination of the linear and logarithmic trapezoidal methods (linear-log trapezoidal rule). The linear trapezoidal method will be applied up to t_{max} and then the logarithmic trapezoidal method will be used after t_{max}. The minimum requirement for the calculation of AUC will be the inclusion of at least three consecutive concentrations above the lower limit of quantitation (LLOQ), with at least one of these concentrations following C_{max}.
- AUC(0-∞) values where the percentage of the total area extrapolated is more than 20% will be flagged. Any AUC(0-∞) value excluded from summary statistics will be noted in the footnote of the summary table.

- Half-life ($t_{1/2}$) will be calculated, when appropriate, based on the apparent terminal log-linear portion of the concentration-time curve. The start of the terminal elimination phase for each subject will be defined by visual inspection and generally will be the first point at which there is no systematic deviation from the log-linear decline in serum concentrations. Half-life will only be calculated when a reliable estimate for this parameter can be obtained comprising of at least 3 data points. If $t_{1/2}$ is estimated over a time window of less than 2 half-lives, the values will be flagged in the data listings. Any $t_{1/2}$ value excluded from summary statistics will be documented in the footnote of the summary table.
- A uniform weighting scheme will be used in the regression analysis of the terminal log-linear portion of the concentration-time curve.
- The parameters based on observed C_{last} will be reported.

Individual PK Parameter Rules

- Only quantifiable concentrations will be used to calculate PK parameters with the exception of special handling of certain concentrations reported below the lower limit of quantitation (BQL). Serum concentrations reported as BQL will be set to a value of zero when all of the following conditions are met:
 - The compound is non-endogenous.
 - The samples are from the initial dose period for a subject or from a subsequent dose period following a suitable wash-out period.
 - The time points occur before the first quantifiable concentration.
- All other BQL concentrations that do not meet the above criteria will be set to missing.
- Also, where two or more consecutive concentrations are BQL towards the end of a profile, the profile will be deemed to have terminated and therefore any further quantifiable concentrations will be set to missing for the calculation of the PK parameters unless it is considered to be a true characteristic of the profile of the drug.

Individual Concentration vs. Time Profiles

- Individual concentrations will be plotted utilizing actual sampling times.
- The terminal point selections will be indicated on a semi-logarithmic plot.

Average Concentration vs. Time Profiles

- The average concentration profiles will be graphed using scheduled (nominal) sampling times.

- The average concentration profiles will be graphed using arithmetic average concentrations.
- The pre-dose average concentration for single-dose data from non-endogenous compounds will be set to zero. Otherwise, only quantifiable concentrations will be used to calculate average concentrations.
- Concentrations at a sampling time exceeding the sampling time window specified in the protocol, or $\pm 10\%$, will be excluded from the average concentration profiles.
- Concentrations excluded from the mean calculation will be documented in the final study report.
- A concentration average will be plotted for a given sampling time only if 2/3 of the individual data at the time point have quantifiable measurements that are within the sampling time window specified in the protocol or $\pm 10\%$. An average concentration estimated with less than 2/3 but more than 3 data points may be displayed on the mean concentration plot if determined to be appropriate and will be documented within the final study report.

Treatment of Outliers during Pharmacokinetic Analysis

Application of this procedure to all PK analyses is not a requirement. Rather, this procedure provides justification for exclusion of data when scientifically appropriate. This procedure describes the methodology for identifying an individual value as an outlier for potential exclusion, but does not require that the value be excluded from analysis. The following methodology will not be used to exclude complete profiles from analysis.

Data within an Individual Profile

A value within an individual profile may be excluded from analysis if any of the following criteria are met:

- For PK profiles during single dosing of non-endogenous compounds, the concentration in a pre-dose sample is quantifiable.
- For any questionable datum that does not satisfy the above criteria, the profile will be evaluated and results reported with and without the suspected datum.

Data between Individual Profiles

1. If $n < 6$, then the dataset is too small to conduct a reliable range test. Data will be analyzed with and without the atypical value, and both sets of results will be reported.
2. If $n \geq 6$, then an objective outlier test will be used to compare the atypical value to other values included in that calculation:
 - a. Transform all values in the calculation to the logarithmic domain.

- b. Find the most extreme value from the arithmetic mean of the log transformed values and exclude that value from the dataset.
- c. Calculate the lower and upper bounds of the range defined by the arithmetic mean $\pm 3*SD$ of the remaining log-transformed values.
- d. If the extreme value is within the range of arithmetic mean $\pm 3*SD$, then it is not an outlier and will be retained in the dataset.
- e. If the extreme value is outside the range of arithmetic mean $\pm 3*SD$, then it is an outlier and will be excluded from analysis.

If the remaining dataset contains another atypical datum suspected to be an outlier and $n \geq 6$ following the exclusion, then repeat step 2 above. This evaluation may be repeated as many times as necessary, excluding only one suspected outlier in each iteration, until all data remaining in the dataset fall within the range of arithmetic mean $\pm 3*SD$ of the log-transformed values.

Reporting of Excluded Values

Individual values excluded as outliers will be documented in the final report. Approval of the final report will connote approval of the exclusion.

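### The SAP is inconsistent on whether between-profile PK outliers must be excluded when n ≥ 6, names the tested set only loosely, and does not require the result with all values kept

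*SAP*

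**What the plan says.** The outlier procedure is in SAP 9.3.1. Its preamble is permissive: "Application of this procedure to all PK analyses is not a requirement", and the method "does not require that the value be excluded from analysis". It offers grounds for exclusion where that is scientifically appropriate. It also sets a limit: "The following methodology will not be used to exclude complete profiles from analysis".

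The part on data between individual profiles then splits by size.

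- For n < 6: "Data will be analyzed with and without the atypical value, and both sets of results will be reported".
- For n ≥ 6, a test is used to "compare the atypical value to other values included in that calculation". The values are logged, the most extreme one is set aside, and limits of mean ± 3 SD are computed from the rest. If the extreme value lies outside them, "then it is an outlier and will be excluded from analysis". The step may be repeated while n stays at 6 or more.

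For a questionable datum within one profile, the SAP asks for "results reported with and without the suspected datum". For between-profile exclusions at n ≥ 6 it asks for no such pair of results, only this: "Individual values excluded as outliers will be documented in the final report".

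SAP 9.3.2 has three kinds of model for log AUC and Cmax: device plus site on all subjects, AI v PFS at each site, and location contrasts within each device. With 10 completers per arm (SAP 7), these use 60, 20 and 30 subjects.

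**The concern.** AUC and Cmax are primary endpoints (Protocol 4), and the AI/PFS ratios with 90% CIs are the bridging result. The SAP should fix in advance which values enter those models. Three gaps stop it from doing so.

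- The preamble and step 2e differ on whether a flagged value must go.
- The comparison set is not named, and neither is what makes a value atypical enough to be tested.
- With-and-without reporting is required where sets are too small to test, but not at n ≥ 6, the size of every planned arm and model.

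The study is open-label (Protocol 7.3), and exclusions are approved by approving the final report. Genuine primary values could therefore be dropped on a statistical test alone, with no all-values ratio required beside the trimmed one.

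**Working it through.** **Inputs.** Geometric CV 55% and 10 completers in each of six arms (SAP 7); device + site model on the log scale with a 90% CI (SAP 9.3.2); steps 2a to 2e, repeated while n ≥ 6 (SAP 9.3.1). Assumptions: the values tested are one AUC or Cmax per subject, and the data are clean log-normal with no aberrant values.

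**1. The plan's own figure.** Log-scale SD = √ln(1 + 0.55²) = √ln 1.3025 = 0.514. The stated precision of 0.48 reproduces as a 10 v 10 comparison: 0.514 × √(1/10 + 1/10) × t(0.95; 18 df) × √(χ²(0.90; 18 df)/18) = 0.514 × 0.447 × 1.734 × 1.202 = 0.479, and 1 − e^(−0.479) = 38%. This confirms the SD. The documents state no operating characteristic for the outlier rule.

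**2. How strict the 3-SD limit is.** The extreme value is left out before the SD is computed, so the effective cut is 3/√(1 + 1/(n − 1)) on a t distribution with n − 2 df. At n = 10 the cut is 3/√(1 + 1/9) = 2.846, and 10 × 2 × P(t₈ > 2.846) = 0.216. Simulated chances that a clean set has its extreme value flagged are 0.216 (n = 10), 0.179 (n = 20), 0.189 (n = 30) and 0.240 (n = 60). A clean set thus loses its extreme value about one time in five, if it is tested.

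**3. Coverage of the nominal 90% CI.** There were 40,000 trials per scenario (Monte Carlo SE about 0.15 to 0.18 points). The extreme value was always tested and always removed when flagged.

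| Model and tested set | True ratio 1 | True ratio 1.25 |
|---|---|---|
| Main model, no exclusion | 90.2% | 89.9% |
| *Closest reading: each model's own input* | | |
| Main model, all 60 | 90.2% | 89.4% |
| AI v PFS at one site, its 20 | 90.2% | 89.0% |
| Locations within a device, its 30 | 90.0% | 90.0% |
| *Other sets, main model* | | |
| Per site | 90.2% | 89.1% |
| Per device | 88.1% | 87.8% |
| Per arm | 86.4% | 86.1% |

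Repeat runs of 8,000 to 40,000 trials at ratio 1 gave 89.8 to 90.8% (all 60), 87.6 to 88.8% (per device) and 85.8 to 86.7% (per arm). If per-arm testing is applied to only some arms, main-model coverage is 89.3% (25% of arms) or 88.2% (50%).

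**4. Effect on the data and the estimate.** At ratio 1, at least one genuine value is lost from the main model in about 24% of trials (all 60), 34% (per device), 44% (per site) or 76% (per arm). The four choices of set give the same data in only 20% of trials. When a value is lost, the ratio moves by a median factor of 1.04 to 1.05 (90th percentile 1.07 to 1.09). There is no bias at ratio 1. At 1.25 the geometric mean estimate is 1.238 with all 60 tested, against 1.248 untrimmed. The mean log half-width at ratio 1 is 0.221 untrimmed, 0.217 (all 60) and 0.212 (per arm).

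**The case against.** The preamble introduces the whole outlier procedure and can be read as governing step 2e, which is then the last step of an optional algorithm. That is a fair reading, and it makes this an ambiguity more than a flat contradiction. But the text states no such precedence, and the reading leaves exclusion of primary values to judgement.

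A reader might infer from the table that the plan's CI really covers about 86%. The documents do not support that. The phrase about values in the calculation points most naturally to each model's input, and no model in SAP 9.3.2 takes a single arm as its input. Per-arm testing could arise only through by-treatment summaries, and nothing says that a value dropped from a summary also leaves the model. The 86% further needs testing and removal in every arm, whereas the SAP starts from a value already judged atypical.

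A reader might also infer a conflict with the protocol, because Protocol 10.3 describes a PK set of all data while SAP 11 reports no changes. That set is limited to subjects with evaluable PK data, a term that is not defined, and SAP 3 says that the SAP supersedes the protocol's statistical considerations. No conflict is shown.

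There are safeguards: excluded values are documented, and SAP 9.1 has all databased data listed, so a reader with the listings could refit the model. That limits the harm but does not put the all-values ratio in the report. Finally, the meaning of values is assumed here, and the bar on excluding complete profiles may restrict what can be dropped.

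**Conclusion.** The point holds as a minor drafting defect with a small but real consequence. The SAP does not settle whether a flagged value must be excluded at n ≥ 6, does not clearly name the tested set, and does not require the all-values result.

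On the closest reading, coverage stays at about 89 to 90% for true ratios between 1 and 1.25. It slips for larger device effects, because pooled testing then trims on the effect itself: at a log ratio of 0.5 (ratio 1.65) it is 88.3% for the main model and 87.0% for the by-site models (8,000 trials). Even on this reading, about 24% of clean trials would lose a genuine value from the main model if the extreme value were always tested. The 86% (per arm) and 88% (per device) figures are upper cases on readings that are not the closest.

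How often the test would be used cannot be known from the documents. The figures rest on clean log-normal data at CV 55% and on reading values as AUC or Cmax per subject, so the benefit of removing a truly aberrant value is not measured. No acceptance margin is attached to the ratios, so no stated decision flips.

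**What to change.** In SAP 9.3.1:

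- Reconcile step 2e with the preamble, so that the text says once whether a flagged value is removed.
- Name the tested set as the input of each model in SAP 9.3.2.
- Use the 3-SD test as a flag.
- At n ≥ 6, report the AUC and Cmax ratios with 90% CIs twice: with all evaluable values as the main result, and without the flagged values. This extends what the SAP already does for n < 6.

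The cost is a few sentences and one extra table. The downside is that an unexplained aberrant value stays in the main model and may widen its CI; the companion analysis shows by how much. Restricting exclusion to documented assay or sampling causes would be a further choice, partly one of preference, and is not needed to settle this point.

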9.3.2 Pharmacokinetic Statistical Methodology

The $AUC(0-\infty)$, $AUC(0-t_{last})$, and C_{max} will be log-transformed and analyzed using a linear fixed-effects model. The model will include device and injection site as fixed effects. The differences between the AI (Test) and PFS (Reference) will be back-transformed to present the ratios of geometric least squares means and the corresponding 90% CI.

Example SAS code:

```
proc mixed data=datain alpha=0.1;
  class device inj_site;
  model log_pk = device inj_site / ddfm=kr alpha=0.1;
  lsmeans device / pdiff cl alpha=0.1;
  ods output lsmeans=lsmeans;
  ods output diff=diffs;
run;
```

The t_{max} of LY3074828 between AI and PFS administrations will be analyzed using a Wilcoxon rank sum test. Estimates of the median difference, 90% CIs, and p-values from the Wilcoxon rank sum test will be calculated.

In addition, the following comparisons will also be made:

- AI versus PFS separately at each injection site (injection site will be removed from the model above)

- Arm versus abdomen and thigh versus abdomen separately for each device (device will be removed from the model above)

Additional PK analyses may be conducted if deemed appropriate.

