 - infertile due to surgical sterilization (hysterectomy, bilateral oophorectomy, or tubal ligation) or congenital anomaly such as Müllerian agenesis; or
 - postmenopausal – defined as either:
 - A woman at least 50 years of age with an intact uterus, not on hormone therapy, who has had either:
 - cessation of menses for at least 1 year; or
 - at least 6 months of spontaneous amenorrhea with a follicle-stimulating hormone >40 mIU/mL; or
 - A woman 55 years of age or older not on hormone therapy, who has had at least 6 months of spontaneous amenorrhea; or
 - A woman at least 55 years of age with a diagnosis of menopause prior to starting hormone-replacement therapy

[2] are between 18 and 65 years of age, inclusive, at time of screening

[3] have a body mass index (BMI) of 18.0 to 32.0 kg/m², inclusive, at time of screening

[4] have clinical laboratory test results within normal reference ranges for the investigative site, or results with acceptable deviations that are judged to be not clinically significant by the investigator

[5] have venous access sufficient to allow for blood sampling as per the protocol

[6] are reliable and willing to make themselves available for the duration of the study and are willing to follow study procedures

[7] are able and willing to give signed informed consent

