10.3. Statistical Analyses

Statistical analysis of this study will be the responsibility of Eli Lilly and Company or its designee.

Pharmacokinetic analyses will be conducted on the full analysis set. This set includes all data from all randomized subjects receiving the dose of LY3074828 with evaluable PK data. Safety analyses will be conducted for all subjects receiving a dose of LY3074828, whether or not they completed all protocol requirements.

Additional exploratory analyses of the data will be conducted as deemed appropriate. Study results may be pooled with the results of other studies for population PK analysis purposes to avoid issues with post-hoc analyses and incomplete disclosures of analyses.

No adjustments for multiple comparisons will be made.

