The primary parameters for analysis will be $AUC(0-\infty)$, $AUC(0-t_{last})$, and C_{max} for LY3074828. The secondary parameter for analysis will be the time to maximum observed drug concentration (t_{max}) of LY3074828. Other noncompartmental parameters, such as half-life associated with the terminal rate constant ($t_{1/2}$), apparent total body clearance of drug calculated after extra-vascular administration (CL/F), and apparent volume of distribution during the terminal phase after extra-vascular administration (V_z/F), may be reported.

10.3.2.2. *Pharmacokinetic Statistical Inference*

The $AUC(0-\infty)$, $AUC(0-t_{last})$, and C_{max} will be log-transformed and analyzed using a linear fixed-effects model. The model will include device and injection location as fixed effects. The dosing regimen differences between AI and PFS administrations will be back-transformed to present the ratios of geometric LS means and the corresponding 90% CI. Comparisons will be made between the 2 devices and then between the 3 injection locations.

The t_{max} of LY3074828 between AI and PFS administrations will be analyzed using a Wilcoxon rank sum test. Estimates of the median difference, 90% CIs, and p-values from the Wilcoxon rank sum test will be calculated.

Additional PK analyses may be conducted if deemed appropriate.

10.3.3. *Pharmacodynamic Analyses*

This section is not applicable for this study.

10.3.4. *Pharmacokinetic/Pharmacodynamic Analyses*

This section is not applicable for this study.

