3. INTRODUCTION

This SAP has been developed after review of the Clinical Study Protocol (final version dated 17 December 2018).

This SAP describes the planned analysis of the safety, tolerability and pharmacokinetic (PK) data from this study. A detailed description of the planned TFLs to be presented in the clinical study report (CSR) is provided in the accompanying TFL shell document.

The intent of this document is to provide guidance for the statistical and PK analyses of data. In general, the analyses are based on information from the protocol, unless they have been modified by agreement between Eli Lilly and Company and Covance Early Clinical (EC) Biometrics. A limited amount of information concerning this study (e.g., objectives, study design) is given to help the reader's interpretation. This SAP must be signed off prior to first subject administration for this study. When the SAP and TFL shells are agreed upon and finalized, they will serve as the template for this study's CSR.

This SAP supersedes the statistical considerations identified in the protocol; where considerations are substantially different, they will be so identified. If additional analyses are required to supplement the planned analyses described in this SAP, they may be performed and will be identified in the CSR. Any substantial deviations from this SAP will be agreed upon between Eli Lilly and Company and Covance EC Biometrics and identified in the CSR. Any minor deviations from the TFLs may not be documented in the CSR.

This SAP is written with consideration of the recommendations outlined in the International Conference on Harmonisation (ICH) E9 Guideline entitled Guidance for Industry: Statistical Principles for Clinical Trials¹ and the ICH E3 Guideline entitled Guidance for Industry: Structure and Content of Clinical Study Reports².

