8. DEFINITION OF ANALYSIS POPULATIONS

The “Safety” population will consist of all subjects who received at least one dose of LY3074828 and have at least one postdose safety assessment.

The “Pharmacokinetic” population will consist of all subjects who received at least one dose of LY3074828 and have evaluable PK data.

All protocol deviations that occur during the study will be considered for their severity/impact and will be taken into consideration when subjects are assigned to analysis populations.

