11. CHANGES FROM THE PROTOCOL SPECIFIED STATISTICAL ANALYSES

There were no changes from the protocol specified statistical analyses.

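### The pooled AI versus PFS exposure model is valid but leaves out screening body weight; prespecifying it would be a cheap gain in precision

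*SAP*

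**What the plan says.** SAP 9.3.2 fits each log-transformed parameter with two terms: "The model will include device and injection site as fixed effects". The example SAS code contains only those two. Protocol 10.3.2.2 gives the same model for the PK parameters, in a sentence also used for the pain scores: "The model will include device and injection location as fixed effects".

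Weight is measured at screening (Protocol section 2), and SAP 9.2 plans only to tabulate it: "body weight, height and body mass index will be summarized and listed". The dose is fixed at 125 mg (Protocol 5.5) and may not be adjusted (7.4). Arms are parallel, with 11 randomized for 10 completers each (5.1). Protocol 7.2 describes a computer-generated schedule and names no stratification factor. Eligible subjects must "have a body mass index (BMI) of 18.0 to 32.0" kg/m².

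The PK population "will consist of all subjects who received at least one dose of LY3074828 and have evaluable PK data", so up to 66 subjects could contribute. On timing, SAP section 3 says: "This SAP must be signed off prior to first subject administration for this study". SAP section 11 says: "There were no changes from the protocol specified statistical analyses".

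**The concern.** With a fixed dose, exposure may fall as weight rises. At any given height the BMI limits admit a 32/18 = 1.78-fold range of weight. A parallel design has no within-subject control, so any variation in exposure due to weight stays in the residual and widens the AI/PFS interval. A chance difference in weight between the device groups would also pass straight into the estimated ratio.

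Neither document prespecifies a weight-adjusted analysis or gives a reason for leaving weight out. Protocol 10.3 says "Study results may be pooled with the results of other studies for population PK analysis purposes", but that is optional, names no covariates, and is not the AI/PFS ratio of SAP 9.3.2. SAP 9.3.2 also permits additional PK analyses. However, an adjustment chosen after an imbalance appears in the demographics table would be post hoc, even if the CSR identifies it. The study is also open-label, and SAP section 10 allows data to be accessed and analysed while it is running.

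What is at stake is the precision of the primary device comparison and freedom from an after-the-fact modelling choice. The validity of the comparison is not in question, and no stated decision margin depends on it.

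**Working it through.** **Inputs from the documents.** Two-sided 90% CI (SAP 9.3.2). Geometric CV 55% for planning, 40 to 55% in earlier studies (SAP 7). 60 completers, 10 per arm, so the pooled device contrast is 30 versus 30 with 60 − 4 = 56 residual df.

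**Assumptions, not in the documents.** Exposure proportional to weight^-b, with b = 0.6 to 1.0 as the working range and b = 0 as the null case. SD of log weight 0.15 to 0.20. As a check on that SD, a normal BMI (mean 25, SD 3 to 4) truncated to 18–32, with a log-height SD of 0.05, gives 0.15 to 0.17. A uniform BMI on 18–32 gives 0.165 before height is added.

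**The plan's own figure.** The log-scale variance is s² = ln(1 + CV²), which is 0.264 (SD 0.514) at 55% and 0.148 (SD 0.385) at 40%. The half-width met with 90% probability is t(0.95, df) × s × √(2/n) × √(χ²(0.90, df)/df). For 10 versus 10, df 18 and CV 55%, this is 0.399 × 1.20 = 0.479, and 1 − exp(−0.479) = 38.1%. So the stated 0.48 and 38% reproduce, but as the AI versus PFS comparison at one site. On the same criterion the pooled contrast is 0.248. The 0.48 is therefore not the baseline for this point.

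**Pooled half-width without weight** (no 90%-probability factor): t(0.95, 56) × s × √(2/30).
- CV 55%: 1.673 × 0.514 × 0.258 = 0.222
- CV 40%: 1.673 × 0.385 × 0.258 = 0.166

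**Effect of adding log weight.** Weight explains R² = (b × SD)²/s² of the variance. The ratio of adjusted to unadjusted half-width is f × √(1 − R²). Here f covers the lost df and the estimation of the slope; f = 1.009 for df 56 to 55.

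| CV | b | R² | Change in CI width | Half-width |
|---|---|---|---|---|
| 55% | 0 | 0 | 0.9% wider | 0.224 |
| 55% | 0.6–1.0 | 3–15% | 0.6–7% narrower | 0.221–0.206 |
| 40% | 0 | 0 | 0.9% wider | 0.168 |
| 40% | 0.6–1.0 | 5–27% | 2–14% narrower | 0.163–0.144 |

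The loss at b = 0 is like losing about 1 of 60 subjects. Break-even R² = 1 − 1/f² = 1.8% (unrounded f), which means b = 0.35–0.47 at CV 55% and 0.26–0.35 at CV 40%. Simulation of both pooled models (8,000 trials per scenario) agrees: +1.0% at b = 0, −0.6 to −7.0% at CV 55% and −1.9 to −13.7% at CV 40%. Unadjusted coverage was 0.896 to 0.906.

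**If all 66 are evaluable** (33 versus 33, df 62 to 61, f = 1.008): 0.8% wider at b = 0; 0.7–7% and 2–14% narrower over the working range.

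**Chance imbalance.** One SD of the difference in mean log weight between devices is SD × √(2/30) = 0.039 to 0.052. An imbalance of k such SDs shifts the log ratio by k × b × SD × √(2/30). For b = 0.6 to 1.0, coverage of the unadjusted CI is:

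| Imbalance | Shift in ratio | CV 55% | CV 40% |
|---|---|---|---|
| None | none | 0.905–0.925 | 0.909–0.945 |
| 1 SD | 2–5% | 0.90 | 0.90 |
| 2 SD | 5–11% | 0.824–0.885 | 0.763–0.873 |

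The chance of an imbalance beyond 2 SD is 4.6%.

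**Separate 10 versus 10 fits.** Here f = 1.032 (df 18 to 17), so adjustment pays only if R² exceeds about 6%, and the CI is 3% wider at b = 0.

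**The case against.** The opposing case is that this is a preference between two valid models.

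- **No error and little effect.** The planned model is unbiased, coverage is right on average, and no margin depends on the result. At the planning CV the lower-limit factor exp(−half-width) moves only from 0.801 to between 0.802 and 0.814.
- **It helps where help is least needed.** The pooled contrast (0.248) is already far tighter than the 0.48 target, while the by-site fits gain nothing.
- **The headline range is favourable.** It lies above break-even throughout. At SD 0.15 and CV 55%, b = 0.5 gives only 0.2% narrower and b = 0.3 gives 0.5% wider. The upper ends need b = 1.0 and SD 0.20; at SD 0.17 they become 4.8% (CV 55%) and 9.5% (CV 40%).
- **Imbalance is a weak argument.** Coverage falls clearly only near 2 SD, and supplementary analyses are already allowed.
- **The remedy displaces the protocol's model.** It would leave the pooled results adjusted and the by-site results unadjusted. A supportive sensitivity analysis would be enough.

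Most of this stands as a limit on size and priority: the typical gain is modest, and it rests on a slope the documents do not give. It does not remove the point. The downside is about 1%, the data are already collected, and the permissive clauses prespecify nothing. The mismatch with the by-site fits is real, but reporting the unadjusted pooled model alongside gives a like-for-like comparison.

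**Conclusion.** The point holds as a recommended improvement. The planned pooled analysis is valid, but it leaves out a baseline covariate that is already collected and plausibly prognostic in a small fixed-dose parallel study. Under the stated assumptions the gain is 0.6 to 7% in CI width at CV 55% and 2 to 14% at CV 40%, against a loss of 0.9% if weight has no effect and a small loss below the break-even slope. It would also protect against an uncommon but material weight imbalance. Confidence is medium, because both the weight–exposure slope and the spread of weight are assumed.

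**What to change.** Before first dosing, add log(screening body weight) as a continuous covariate to the pooled AI versus PFS models for AUC(0-∞), AUC(0-tlast) and Cmax. Name the adjusted model as primary for all three, and report the device-plus-site model as a sensitivity analysis. Enter this in SAP section 11 as a change from the protocol model.

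Keep the planned by-site and by-device fits unadjusted. If weight-adjusted versions are wanted, take them from one six-arm model with a common weight slope and label them supportive.

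The cost is one model term and one section 11 entry, with no new data or subjects. The term uses 1 of 56 df (1 of 62 if all 66 are evaluable) and makes the pooled CI about 1% wider if weight explains nothing.
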